5.4. Data Collection

Table 1 depicts the assessments, measurements, and time points for the data collection. We will administer patient-reported measures for 48 weeks from enrollment. We selected a longer administration period in the current study as the median survival for patients with lung cancer is now approximately one year. The study assessment battery takes approximately 20 minutes to complete.

Table 1. Summary of data collection instruments and time-points.

Self-Report Measure	Baseline	Every 6 weeks*	Week 12	Week 24	Week 36	Week 48
Demographic Questionnaire	X					
Self-Administered Comorbidity Questionnaire (SCQ)	X					
Functional Assessment of Cancer Therapy-Lung (FACT-L)*	X	X*	X	X	X	X
Patient Health Questionnaire-9 (PHQ-9)	X		X	X	X	X
Prognosis and Treatment Perceptions Questionnaire (PTPQ)	X		X	X	X	X
Brief Cope	X		X	X	X	X
EuroQol – 5 Dimension (EQ-5D)	X		X	X	X	X
Support Service Utilization Item					X	

*Step 1 patients will complete the FACT-L every 6 weeks for a minimum of 12 months and up to 18 months from enrollment

5.4.1. Data from Electronic Health Record:

Clinical information regarding tumor type (NSCLC, small cell lung cancer, and mesothelioma), current treatment regimen, date of diagnosis of incurable disease,

previous diagnosis of early stage disease, tumor genotype, and ECOG Performance Status will be collected at baseline.

Health care utilization data will be collected after death or at 12-months from the date the last patient enrolled on the study. We will collect data on: (1) outpatient and inpatient PC visits; (2) chemotherapy and radiation therapy administration; and (3) emergency department, hospital and intensive care unit admissions. EOL care measures will include referrals to and length of stay on hospice and location of death.

5.4.2. PC Cost and Resource Utilization Data:

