7.5. Analysis Plan

The primary endpoint of the study is to establish that stepped PC is non-inferior to early integrated PC in QOL, as measured by the FACT-L at week-24. We will begin with descriptive and graphical summaries of the endpoints to evaluate whether the normality assumption is reasonable or if transformation is necessary. Based upon our prior study demonstrating statistical and clinically meaningful between group differences in the FACT-L at 24-weeks, the primary endpoint to compare patient FACT-L scores at week-24 between the study groups using a linear regression model controlling for randomization stratification factors, baseline values, and demographic and clinical factors (as necessary for any imbalances in baseline variables). We will also use linear mixed models of the longitudinal data, allowing us to account for dependency among means over time and to control for demographic and clinical factors when examining change between groups in QOL across multiple time points. We will also compare the number of PC visits between the two groups to ensure that the stepped PC model led to a reduction in PC visits.

We will compare depression (PHQ-9) and coping strategies (Brief Cope, including higher-order factors of the Brief Cope in our sample⁵²: active coping & avoidant coping) at week-24 between groups using linear regression models controlling for randomization

stratification factors, baseline values and selected demographic and clinical factors. We will then evaluate linear mixed models of the longitudinal data, as described above, to examine changes in these outcomes between groups across multiple time points.

To compare illness understanding as measured by the PTPQ between the two groups at week-24, we will analyze appropriate items using the appropriate model for the outcome of interest (e.g., linear regression or generalized linear models with an identity link function and binary response probability distribution) with adjustment for randomization stratification factors and any demographic and clinical factors that are imbalanced to assess differences between groups.

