**Table 1. Study Questionnaires**

Self-report measure	Baseline	Every 6 weeks	Weeks 12, 24, 36 & 48	Scoring
Demographics	X			n/a
SCQ	X			Range: 0-45 (higher is worse medical condition)
FACT-L	X	X 	X	Range: 0-136 (higher is better QOL)
PHQ-9	X		X	Range: 0-27 (higher is worse depression)
PTPQ	X		X	n/a

Brief Cope	X		X	Range: 2-8 for each facet (higher is more engagement in coping style)
EQ-5D	X		X	VAS Range: 0-100 (higher is better health state)
Support Service Utilization Item			X 	

 Step 1 patients completed FACT-L every 6 weeks for up to 18 months from enrollment.

 Collected only at week 24.

EQ-5D, EuroQol—5 Dimension; FACT-L, Functional Assessment of Cancer Therapy-Lung; PHQ-9, Patient Health Questionnaire-9; PTPQ, Prognosis and Treatment Perceptions Questionnaire; SCQ, Self-administered Comorbidity Questionnaire.

The primary outcome is patient-reported quality of life at 24 weeks from enrollment, as measured by the FACT-L.

The secondary outcomes are:

1. Patient report of patient-clinician communication about EOL care preference using the following item on the PTPQ: “Have you and your doctors discussed any particular wishes you have about the care you would want to receive if you were dying?” analyzed as “yes” versus “no.” The patient’s final assessment will be used.
2. Length of stay on hospice (in days) among patients who die during the study, as documented in the EHR.
3. PC resource utilization; specifically, the number of outpatient PC visits per patient during the study, as documented in the EHR.

The exploratory outcomes are:

1. Rate of change in quality of life from baseline to week 48, as measured by the FACT-L.
2. Cost-effectiveness as assessed by costs relative to quality adjusted life years. **Note:** Plans for the analysis of cost-effectiveness are not described in this SAP.
3. Patient-reported coping strategies at week 24, as measured by eight subscales of the Brief Cope, including subscales measuring emotional support, positive reframing, active coping, acceptance, self-blame, denial, spiritual coping, and behavioral disengagement, as well as higher-order factors reflecting active coping and avoidant coping).
4. Patient-reported prognostic understanding at week 24, based on relevant items on the PTPQ, including:
  - a. Patient’s primary goal of current cancer care. Responses will be dichotomized based on whether the patient selected “to cure my cancer” versus any of the other options.

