### *Adjustment of the Intervention Effect*

The primary analyses for all outcomes will be adjusted for the randomization stratification variables: study site (MGH vs Duke vs Penn) and cancer diagnosis (NSCLC vs SCLC and mesothelioma). Small strata will be combined as needed to ensure numeric stability of model estimates. If needed, sensitivity analyses will additionally adjust for baseline characteristics that are imbalanced between treatment groups. Imbalanced characteristics will be identified *a priori* by examining the distributions of baseline characteristics known to be associated with the primary and secondary outcomes by intervention group. Characteristics that are imbalanced to an extent that is considered clinically meaningful will be included as adjustment covariates in addition to study site and cancer diagnosis.

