## **9. Statistical Analysis**

### *Primary Outcome*

The primary outcome is patient-reported quality of life at week 24, as measured by the FACT-L. The difference in week 24 means between intervention groups will be estimated using a linear regression model with group assignment (stepped PC vs early integrated PC) and baseline FACT-L score, as well as randomization stratification factors, as main effects. Using the pre-specified non-inferiority margin of 4.5 points, non-inferiority of stepped PC will be established if the lower limit of the 90% confidence interval (CI) for the estimated difference in means is greater than -4.5. The corresponding p-value for non-inferiority will be calculated using a one-sided test of the estimated difference in means against a null value of -4.5 with a significance level of 0.05. Model-based estimates of the mean with 95% CI in each group, the difference in means between groups and its 90% CI, and the p-value will be reported.

To accompany the approach described above, we will also use a linear mixed effects regression model to estimate the difference in week 24 means between intervention groups. This model will utilize FACT-L scores at baseline, week 12, and week 24, with estimation via maximum likelihood. The model will include fixed effects for group assignment (stepped PC vs early integrated PC), time from baseline (in weeks), time-by-group interaction, and randomization stratification factors, as well as random intercepts for each patient. A contrast will be used to estimate the difference in means at week 24, and this estimate will be evaluated for non-inferiority in the same manner described above. This will be reported as a sensitivity analysis for evaluating non-inferiority for the primary outcome.

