#### *Exploratory Outcomes*

The rate of change in quality of life from baseline to week 48 (assessed by the FACT-L) will be compared between groups using a linear mixed effects regression model. This model will utilize FACT-L scores at each timepoint, with estimation via maximum likelihood. The model will include fixed effects for group assignment (stepped PC vs early integrated PC), time from baseline (in weeks), time-by-group interaction, and randomization stratification factors, as well as random intercepts for each patient.

Model-based estimates of the slope with 95% CI in each group and the difference in slopes between groups and its 95% CI will be reported.

The difference in means between intervention groups in patient-reported depression symptoms (assessed by PHQ-9) and coping strategies (assessed by subscales and higher-order factors of Brief Cope) at week 24, will be estimated for each outcome using a linear regression model with group assignment (stepped PC vs early integrated PC) and baseline score, as well as randomization stratification factors, as main effects. Model-based estimates of the mean with 95% CI in each group and the difference in means between groups and its 95% CI will be reported.

Rates of prognostic understanding at week 24, based on PTPQ items eliciting the patient's goal of cancer care ("to cure my cancer" vs any other option) and the patient's assessment of curability ("yes" vs "no") will be compared using generalized linear models specified with an identity link function and binomial response probability distribution. Model-based estimates of the rate with 95% CI in each group and the difference in rates between groups and its 95% CI will be reported.

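### The prognostic-understanding models leave out the patient's baseline answer to the same item, which gives up some precision in an exploratory outcome

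*SAP*

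**What the plan says.** The Exploratory Outcomes part of SAP section 9 states that rates of the two PTPQ items "will be compared using generalized linear models specified with an identity link function and binomial response probability distribution". That paragraph names no covariates. The SAP section Adjustment of the Intervention Effect supplies them: "The primary analyses for all outcomes will be adjusted for the randomization stratification variables", namely site and diagnosis. Protocol 7.5 gives the PTPQ items a similar list, a model "with adjustment for randomization stratification factors and any demographic and clinical factors that are imbalanced to assess differences between groups". The baseline answer to the item appears in neither document's list.

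The other week-24 patient-reported outcomes are handled differently. PHQ-9 and Brief Cope use a "linear regression model with group assignment (stepped PC vs early integrated PC) and baseline score, as well as randomization stratification factors, as main effects". The primary FACT-L regression includes "baseline FACT-L score, as well as randomization stratification factors, as main effects".

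The baseline answer should exist. Table 1 in both documents schedules the PTPQ at baseline, and Protocol 4.4 and SAP section 4 place completion of baseline measures before randomization.

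SAP section 6 defines the outcome as "Patient-reported prognostic understanding at week 24, based on relevant items on the PTPQ". Addendum item 2 (December 2023) changes this to the week-24 answer, or the week-12 answer where week 24 is missing, and adds no covariate. Under Significance Level and Multiplicity Adjustment, exploratory outcomes carry no multiplicity correction and are to be reported mainly as estimates with intervals.

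**The concern.** A patient's belief about curability before randomization plausibly predicts the same belief a few months later. Where it does, leaving it out of the model makes the between-group interval wider than the collected data require. For an outcome with no test and no margin, the interval is the main product, so its width is what is at stake. The SAP makes this adjustment for the neighbouring patient-reported outcomes and gives no reason for treating these two items differently.

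**Working it through.** **1. Figures in the plan.** Neither document states a sample size, power or precision for prognostic understanding, so there is no figure of its own to reproduce. The trial's general sample size does reproduce. With margin 4.5, SD 17.5, true difference 0, one-sided alpha 0.05 and 80% power, n = 2 x (1.645 + 0.842)^2 x 17.5^2 / 4.5^2 = 187.005, rounded up to 188 per group (power 80.2%). It is used here only as background.

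**2. Patients available.** SAP section 7 plans 255 per group with 36% missing at week 24, so 255 x 0.64 = 163 per group (the protocol's 35% gives 166). The addendum's week-12 substitution raises this by an amount the documents do not give. The range is therefore 163 (week-24 completers only) to 255 (ceiling).

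**3. Unadjusted precision.** The 95% half-width of a risk difference is 1.96 x sqrt(2p(1 - p)/n). The rate p is not in the documents. At an assumed p = 0.35:
- n = 163: 1.96 x sqrt(2 x 0.35 x 0.65 / 163) = 10.4 points
- n = 255: 1.96 x sqrt(2 x 0.35 x 0.65 / 255) = 8.3 points

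At n = 163, assumed rates of 20%, 30%, 40% and 50% give 8.7, 9.9, 10.6 and 10.9 points.

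**4. Effect of adding the baseline answer.** The standard error is multiplied by about sqrt(1 - r^2), where r is the correlation between the baseline and follow-up answers. The equivalent gain in patients is 1/(1 - r^2) - 1. All values of r are assumed; p = 0.35.

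| r | sqrt(1 - r^2) | Interval narrower by | Half-width, n = 163 | Half-width, n = 255 | Equivalent gain in patients |
|---|---|---|---|---|---|
| 0 | 1.000 | 0% | 10.4 | 8.3 | 0% |
| 0.1 | 0.995 | 0.5% | 10.3 | 8.2 | 1% |
| 0.3 | 0.954 | 5% | 9.9 | 7.9 | 10% |
| 0.5 | 0.866 | 13% | 9.0 | 7.2 | 33% |
| 0.6 | 0.800 | 20% | 8.3 | 6.6 | 56% |

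The relative gain depends only on r. The absolute widths also depend on p and n.

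**5. Simulation check.** For each r, 1,000 trials were simulated with 163 per arm, an assumed 40% rate, no true difference, and an identity-link binomial model containing site and diagnosis, fitted with and without the baseline answer.

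| r | SD ratio, adjusted / unadjusted | sqrt(1 - r^2) | Failed or unusable fits per 1,000 |
|---|---|---|---|
| 0 | 1.000 | 1.000 | 0 |
| 0.3 | 0.952 | 0.954 | 1 |
| 0.5 | 0.865 | 0.866 | 7 |
| 0.7 | 0.701 | 0.714 | 46 |

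Neither model showed bias: mean estimates lay between -0.1 and 0.3 points of the true zero, which is within simulation error. Adjustment cost no precision at r = 0. At r = 0.7 the mean model standard error fell to 0.656 of the unadjusted one, while the actual spread fell only to 0.701. The reported standard error was thus about 6% too small (0.656 / 0.701 = 0.94) relative to the unadjusted model.

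**6. Target of estimation.** The risk difference is collapsible, so adding a baseline covariate does not change the quantity being estimated.

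**The case against.** The strongest reply is that this is a choice, not a mistake. Protocol 7.5 lists baseline values for PHQ-9 and Brief Cope but not for the PTPQ items, and the SAP keeps that split. The secondary outcome on end-of-life communication, also a yes/no PTPQ item, is likewise modelled without its baseline answer. The outcome is exploratory and no trial conclusion depends on it. Identity-link fits become less stable with a strong predictor, exactly where the gain is largest. Participants may decline any question (Protocol 4.3) and the SAP has no rule for a missing single PTPQ item, so a careless fix could drop patients. All of this stands. It lowers the priority and shapes the remedy, but it does not show that the baseline answer is better left out.

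Three stronger readings are tempting and are not supported:

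- A reader might infer from the silent paragraph that these models are unadjusted. They are not: the general rule brings in site and diagnosis.
- A reader might infer that the omission biases the comparison or leaves chance imbalance wholly unaddressed. Randomization protects the unadjusted estimate from bias. Both documents also provide for adjusting for imbalanced characteristics, although the SAP does so only as a conditional sensitivity analysis, screened on factors tied to primary and secondary outcomes, and neither names the baseline answer.
- A reader might take a gain of a third or more in effective sample size as established. The documents contain no correlation, and at r = 0.1 the gain is 1%.

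**Conclusion.** The point holds as a minor efficiency loss in an exploratory outcome. The two prognostic-understanding models adjust for site and diagnosis but not for the baseline answer to the same item, which is collected by design. The cost is an interval wider than it need be: negligible if the baseline answer predicts weakly (r near 0.1), and 13% to 20% removable if r is 0.5 to 0.6. It is not a bias or type I error problem. The size rests on an assumed correlation. The absolute widths also rest on an assumed 35% rate and on 163 to 255 patients per group, where 163 is a lower bound because of the week-12 substitution.

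**What to change.** In both models, include the baseline response to the same PTPQ item and the randomization strata as main effects, using the addendum's outcome definition (week 24, or week 12 if week 24 is missing). Keep patients whose baseline item is blank, for example through a missing-response category. State in advance that if the identity-link fit does not converge or is unstable, the standardized risk difference from a logistic model with the same covariates will be reported.

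No new data are needed. The costs are somewhat less stable identity-link fits when the baseline answer is strongly predictive, which the fallback handles, and one more dated addendum item after SAP finalization in an unblinded trial. If outcome data by arm have already been analysed, the adjusted model should be labelled a sensitivity analysis.
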